## 4.2 Exclusion criteria

1. Use of other investigational drugs at the time of enrollment, or within 5 half-lives of enrollment, or until the expected PD effect has returned to baseline, whichever is longer; or longer if required by local regulations.
2. History of hypersensitivity to the study drug or to drugs of similar chemical classes.
3. As per the investigator's judgement, a history of tobacco, drug or alcohol abuse that will compromise the patient's ability to participate in this study.
4. Currently pregnant, pregnant within the last 6 months, or nursing (lactating) women.
5. Women of child-bearing potential, defined as all women physiologically capable of becoming pregnant. Women are considered post-menopausal and not of child bearing potential if they have had 12 months of natural (spontaneous) amenorrhea with an appropriate clinical profile (e.g. age appropriate, history of vasomotor symptoms) or have had surgical bilateral oophorectomy (with or without hysterectomy) or tubal ligation at least six weeks ago. In the case of oophorectomy alone, only when the reproductive status of the woman has been confirmed by follow up hormone level assessment is she considered not of child bearing potential.
6. Sexually active males must use a condom during intercourse while taking drug and for 10 hours (*= 5 times the terminal half-life of investigational medication*) after stopping CLR325 and should not father a child in this period. A condom is required to be used also by vasectomized men in order to prevent delivery of the drug via seminal fluid.
7. Chronic infection with Hepatitis B (HBV) or Hepatitis C (HCV). A positive Hepatitis B surface antigen (HBsAg) test excludes a patient. Patients with a positive Hepatitis C antibody test should have HCV RNA levels measured. Patients with positive (detectable) HCV RNA should be excluded.
8. Patients with a history of chronic hepatitis of any non-cardiac etiology.
9. Patients with values of AST or ALT >100 U/L measured within the last 3 months before randomization.
10. Presence of impaired renal function as indicated by clinically significant abnormal creatinine values (eGFR < 30 ml/min/1.73m^2 calculated using the MDRD equation).
11. Known family history or known presence of long QT syndrome.
12. History of any active, clinically significant cardiac tachyarrhythmia (such as recurrent atrial fibrillation with rapid ventricular response) within the last year. Note that patients with chronic atrial fibrillation with a pulse rate ≤ 100 bpm should not be excluded. Anticoagulation for patients with atrial fibrillation should be managed per usual clinical practice for patients undergoing right heart catheterization.
13. Patients with known significant valvular heart diseases indicated by the following:
  - severe aortic stenosis (Aortic Valve Area < 1.0 cm^2 or peak gradient > 50 mm Hg as determined by echocardiography)
  - severe mitral stenosis

14. Patients with history of acute coronary syndrome within the last 60 days as determined by both clinical and enzymatic criteria.
15. For echocardiography-based cohorts only, patients admitted to an inpatient setting for acute decompensated heart failure within the last 30 days.
16. Patients who have received an intravenous infusion of a cardiac inotrope (e.g., dobutamine or milrinone) in the last 24 hours prior to randomization.
17. For PA catheter cohorts, patients with a pulmonary capillary wedge pressure of <10 mm Hg at baseline. For echocardiographic cohorts, patients with a lateral E/E' ratio of <7 on their baseline echocardiogram. For patients in whom a lateral E/E' ratio cannot be determined (e.g., patients in atrial fibrillation), a central venous pressure of <5mm Hg on baseline echocardiogram as determined by inferior vena cava criteria.
18. Patients with any significant change in their dose of their ACE, ARB, mineralocorticoid receptor antagonist, diuretic, or  $\beta$ -blocker within the last 12 hours. Patients with minor changes in their heart failure regimen may be eligible if deemed clinically stable by both the investigator and sponsor.
19. Any surgical or medical condition which in the opinion of the investigator may place the subject at higher risk from his/her participation in the study.

No additional exclusions may be applied by the investigator, in order to ensure that the study population will be representative of all eligible patients.

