## 1 Introduction

Acute decompensated heart failure is commonly caused by deteriorating cardiac function that leads to unplanned, often urgent, medical intervention. There are ~500,000 hospitalizations annually for acute decompensated heart failure in the USA and the 30-day mortality following hospitalization is up to 11% (Jong et al 2002). Patients typically experience fatigue, breathlessness, fluid retention, and chest pain. The common treatment approach of vasodilators and diuretics is ineffective in a substantial proportion of heart failure patients with a reduced ejection fraction due to a predominant deficit in cardiac contractility. Intravenous inotropes, including dobutamine ( $\beta$ -agonist), and milrinone/amrinone (PDEIII inhibitors) are used to augment cardiac output in these patients and are associated with increased risk of arrhythmia and mortality (Felker and O'Connor 2001). In contrast, digoxin does not increase all-cause mortality, and reduces heart failure hospitalizations in patients with heart failure (Digitalis Investigation 1997), but it is a weak inotrope with a narrow therapeutic index. Therefore, new inotropic therapies that can effectively enhance cardiac function without increasing the risk of arrhythmias and/or mortality are urgently needed for patients with heart failure.

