# **7 Discontinuation and study completion**

## **7.1 Discontinuation of study treatment**

Patients may voluntarily discontinue study treatment for any reason at any time.

The investigator must discontinue study treatment for a given patient if, on balance, he/she believes that continuation would be detrimental to the patient's well-being.

Study treatment must be discontinued under any of the following circumstances:

- Patient withdraws consent
- Any protocol deviation that results in a significant risk to the subject's safety
- Emergence of the following adverse events:
  - Acute myocardial infarction
  - Worsening myocardial ischemia
  - Sustained atrial or ventricular tachycardia
  - AICD discharge or anti-tachycardia pacing by the AICD in a patient with an AICD in place
  - An increase in non-sustained ventricular tachycardia or ventricular ectopy deemed clinically concerning by the investigator
  - Severe allergic reaction (e.g., angioedema)
- Occurrence of persistent elevation of systolic blood pressure to >180 mmHg or diastolic blood pressure >100 mm Hg
- Occurrence of symptomatic hypotension requiring persistent medical intervention (i.e. fluid replacement or inotropic therapy). Note that change of patient position does not qualify as an intervention if the need for this change in position is not persistent
- A drop in cardiac index of > 30% as compared to the average of all cardiac index measurements obtained prior to the start of infusion. All cardiac index values showing a 30% drop from baseline should be repeated and study drug terminated only if values are confirmed.
- Any clinically significant cardiac arrhythmia resulting in hemodynamic instability or requiring medical intervention to terminate
- Any of the following laboratory abnormalities:
  - Elevation in white blood cell count to greater than 2.5x above the ULN
  - Elevated AST or ALT > 8x above the ULN
  - Elevated AST or ALT > 3x above the ULN and TBL > 2x the ULN but without an increase in ALP to >2x the ULN
  - Elevated AST or ALT > 3x above the ULN and symptoms of malaise, fatigue, abdominal pain, nausea, vomiting, or rash with eosinophilia.

The appropriate personnel from the site and Novartis will assess whether study treatment should be discontinued for any patient whose treatment code has been broken inadvertently for any reason.

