> 2 × ULN (in the absence of known bone pathology)	
 
Repeat LFT within 48 hours
 
If elevation persists, establish causality
 
Complete liver CRF
 
	
Investigator discretion
 
Monitor LFT within 1 to 4 weeks or at next visit

TBL (isolated)		
> 2 × ULN (in the absence of known Gilbert syndrome)	
 
Repeat LFT within 48 hours
 
If elevation persists, discontinue the study drug immediately
 
Hospitalize if clinically appropriate
 
Establish causality
 
Complete liver CRF
 
	
ALT, AST, TBL, Alb, PT/INR, ALP and γGT until resolutionc (frequency at investigator discretion)
 
Test for hemolysis (e.g. reticulocytes, haptoglobin, unconjugated [indirect] bilirubin)

> 1.5 to ≤ 2 × ULN (patient is asymptomatic)	
 
Repeat LFT within the next week
 
If elevation is confirmed, initiate close observation of the patient
 
	
Investigator discretion
 
Monitor LFT within 1 to 4 weeks or at next visit

Jaundice	
 
Discontinue the study drug immediately
 
Hospitalize the patient
 
Establish causality
 
Complete liver CRF
 
	
ALT, AST, TBL, Alb, PT/INR, ALP and γGT until resolutionc (frequency at investigator discretion)

Any AE potentially indicative of a liver toxicity*	
 
Consider study drug interruption or discontinuation
 
Hospitalization if clinically appropriate
 
Establish causality
 
Complete liver CRF
 
	
Investigator discretion

\*These events cover the following: hepatic failure, fibrosis and cirrhosis, and other liver damage-related conditions; the non-infectious hepatitis; the benign, malignant and unspecified liver neoplasms

a Elevated ALT/AST > 3 × ULN and TBL > 2 × ULN but without notable increase in ALP to > 2 × ULN

b (General) malaise, fatigue, abdominal pain, nausea, or vomiting, or rash with eosinophilia

c Resolution is defined as an outcome of one of the following: (1) return to baseline values, (2) stable values at three subsequent monitoring visits at least 2 weeks apart, (3) remain at elevated level after a maximum of 6 months, (4) liver transplantation, and (5) death.

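### Entry criteria set no limit on bilirubin or ALP, yet the liver rules act on fixed ULN multiples of both with no reference to the pre-dose value, so an eligible patient can already be a liver event before dosing

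*Protocol*

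**What the plan says.** **Entry (Protocol Section 4.2).** Criterion 9 excludes "Patients with values of AST or ALT >100 U/L measured within the last 3 months before randomization". Criterion 8 excludes "Patients with a history of chronic hepatitis of any non-cardiac etiology", so chronic hepatitis of cardiac cause is not excluded. Sections 4.1 and 4.2 contain no limit on TBL, ALP or INR. Criterion 19 leaves the investigator a discretionary exclusion: "Any surgical or medical condition which in the opinion of the investigator may place the subject at higher risk". The section then bars any further exclusions by the investigator.

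**Liver events and actions (Section 9.3).** In Table 9-1, TBL above 2 x ULN alone is a liver event (known Gilbert syndrome exempted), and so is ALP above 2 x ULN alone (known bone pathology exempted). For isolated TBL above 2 x ULN, Table 9-2 asks for a repeat within 48 hours and then: "If elevation persists, discontinue the study drug immediately". Baseline appears only in the footnote that defines resolution.

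**Mandatory discontinuation (Section 7.1).** The list has three liver rules: AST/ALT above 8 x ULN; AST/ALT above 3 x ULN with TBL above 2 x ULN and no ALP rise above 2 x ULN; and "Elevated AST or ALT > 3x above the ULN and symptoms of malaise, fatigue, abdominal pain, nausea, vomiting, or rash with eosinophilia". The text of Section 9.3 sends the reader to Section 7.1 for discontinuation after a liver event, if appropriate.

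**Study pause (Section 7.4).** Two or more infusions discontinued for safety or tolerability pause dosing. The rule is not restricted to one arm or one cohort.

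**The concern.** A discontinuation rule is meant to react to something that happens on treatment. These liver limits are fixed multiples of ULN, and for TBL and ALP the entry criteria do nothing to keep patients below them. The population makes this more than theoretical. Criterion 8 leaves liver disease of cardiac origin in. Criterion 17 removes patients with low filling pressures. Section 3.1 lets later cohorts take patients stabilized after acute decompensation.

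At stake is an infusion stopped for a condition the patient brought into the trial, whichever arm was assigned. In a cohort with 6 active patients, one such stop on active drug loses the full 18-hour exposure and PK profile of 1/6 = 17% of them; with 4 active patients (Section 11.6) it is 1/4 = 25%. Two such stops anywhere in the study trigger an unblinded safety review that reflects eligibility rather than the drug.

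**Working it through.** The plan's only figure that can be recomputed is in Section 11.6: 1 − 0.8^6 = 0.738 (stated 74%) and 1 − 0.8^4 = 0.590 (stated 60%). It agrees to within a point and has no bearing here.

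**1. Entry against liver rules**

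| Finding | Entry limit (4.1, 4.2) | Liver event (Table 9-1) | Discontinuation (Table 9-2) | In the 7.1 list? |
|---|---|---|---|---|
| TBL alone | none | > 2 x ULN | > 2 x ULN, if it persists on repeat | no |
| ALP alone | none | > 2 x ULN | none | no |
| Jaundice | none | any | at once | no |
| AST/ALT with INR | 100 U/L; INR none | > 3 x ULN and INR > 1.5 | at once | no |
| AST/ALT with TBL | 100 U/L; TBL none | > 3 x and > 2 x ULN, ALP not > 2 x | at once | yes |
| AST/ALT with symptoms | 100 U/L | > 3 x ULN | at once | yes |
| AST/ALT alone | 100 U/L | > 5 x ULN | > 8 x ULN, at once | yes (> 8 x) |

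No row refers to the pre-dose value. Other rules in the same protocol do: the creatinine alerts in Section 9.4 are percentage rises from baseline, and the cardiac index rule in Section 7.1 is a fall from the mean of the pre-infusion readings.

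The first two rows need no assumption. Whatever the ULN, an eligible patient can exceed 2 x ULN for TBL or ALP on the Day 1 pre-dose sample.

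**2. Can the TBL row act within an 18-hour infusion?** Table 8-1 schedules chemistry at baseline and at 6, 12, 18 and 24 h. A raised baseline TBL that is still raised at 6 h has been repeated within 48 hours with 18 − 6 = 12 h of infusion left; at 12 h, 18 − 12 = 6 h are left. So it can, provided the result is back in time. The protocol gives no turnaround time.

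**3. Does the 100 U/L limit overlap the AST/ALT rules?** The highest eligible value is 100 U/L, which exceeds k x ULN only if ULN < 100/k:

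- k = 3: ULN < 33.3 U/L
- k = 5: ULN < 20 U/L
- k = 8: ULN < 12.5 U/L

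The protocol gives no ULN. Over an assumed range:

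| Assumed ULN (U/L) | 100 U/L as multiple of ULN | Eligible values above 3 x ULN |
|---|---|---|
| 30 | 3.33 | above 90, up to 100 |
| 32 | 3.12 | above 96, up to 100 |
| 33 | 3.03 | above 99, up to 100 |
| 35 | 2.86 | none |
| 40 | 2.50 | none |
| 45 | 2.22 | none |

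The combinations above 3 x ULN are within reach at entry only for ULN below 33.3 U/L, and for ULN of 30 or more only in a narrow band. The rules above 5 x and 8 x ULN are out of reach for any ULN of 20 or more.

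**4. Scale of the pause, on assumption only.** Let q be the share of randomized patients who enter with TBL above 2 x ULN. The protocol gives no value. If patients are independent, the chance of at least two among n is 1 − (1 − q)^n − nq(1 − q)^(n−1):

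| q (assumed) | n = 8 (first cohort) | n = 40 (study maximum) |
|---|---|---|
| 2% | 0.010 | 0.190 |
| 5% | 0.057 | 0.601 |
| 10% | 0.187 | 0.920 |
| 15% | 0.343 | 0.988 |

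These are ceilings for this route, since they take every such patient to be confirmed and stopped during the infusion.

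**The case against.** Much can be said on the other side.

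- **A reader might infer that entry contradicts the Section 7.1 stopping rules.** The document does not show that. Every liver rule in 7.1 needs AST/ALT above 3 x or 8 x ULN, and criterion 9 keeps eligible patients at or below 3 x ULN wherever the ULN is 33.3 U/L or more. At an assumed ULN of 35, crossing 105 U/L from 100 U/L is a change after dosing, which the rule exists to catch.
- **A reader might infer that anticoagulation alone triggers a rule,** since criterion 12 says "Anticoagulation for patients with atrial fibrillation should be managed per usual clinical practice". It does not: INR above 1.5 counts only together with AST/ALT above 3 x ULN.
- **A reader might add fatigue as a near-universal symptom,** citing Section 1: "Patients typically experience fatigue, breathlessness, fluid retention, and chest pain". That sentence describes acute decompensated heart failure, whereas the trial enrols stable patients.
- **A reader might infer that the primary adverse event counts are inflated.** They may be, but not automatically. Section 9.1 makes a laboratory value an adverse event only if it causes symptoms, is clinically significant or needs therapy. Section 8.2 allows abnormalities from before consent to be recorded as medical history. Section 9.3 requires other causes to be considered. The effect also falls on both arms alike, so no between-arm bias follows.
- **Discretion softens the conflict.** Criterion 19 allows exclusion, Section 9.3 qualifies discontinuation, and a pause under 7.4 leads to a review that can look at baseline values.

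The first four points stand and limit the concern to TBL and ALP. The last stands only in part. Discretion sets no limit and will vary by site, while the TBL row of Table 9-2 is written as an instruction.

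**Conclusion.** The point holds for TBL and ALP at any ULN. An eligible patient can be a Table 9-1 liver event on the pre-dose sample. For TBL, the same sample also meets the first part of a discontinuation rule that a stable value can complete during the infusion, in either arm, and that stop counts towards the Section 7.4 pause. For AST/ALT the overlap is conditional on a laboratory ULN below 33.3 U/L, which the protocol does not state.

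A related inconsistency needs no assumption. Table 9-2 discontinues for persistent isolated TBL, for jaundice, and for AST/ALT above 3 x ULN with INR above 1.5. None of the three is in the Section 7.1 list to which Section 9.3 refers, so a site cannot tell which list governs.

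The frequency cannot be derived from the protocol. The risk is to exposure, PK completeness and the meaning of a pause, not to the fairness of the comparison. Some of the risk text is redacted, so a reason for the liver criteria may exist that is not visible.

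**What to change.** Reconcile Sections 4.2, 7.1 and 9.3 (Tables 9-1 and 9-2) so that no patient satisfies entry and a liver event or discontinuation rule on the same pre-dose sample. This can be done through the entry criteria, or by stating how the liver limits are read when the pre-dose value is already abnormal. In the same amendment, make the Section 7.1 list and the discontinuation rows of Table 9-2 agree, or say which governs. The choice of rule is the sponsor's, and no threshold is proposed here.

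The cost is amendment wording: chemistry and coagulation are already drawn at screening and baseline. If the entry route is chosen, a few patients with hepatic congestion may become ineligible.

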## **5 Restrictions for Study Subjects**

During recruitment, screening/informed consent review, and baseline visit, the subjects must be informed and reminded of the following restrictions:

### **5.1 Contraception requirements**

Please refer to exclusion criteria ([Section 4](#)) for details of contraception requirements for the study.

### **5.2 Prohibited treatment**

Any cardiac intravenous inotrope such as dobutamine or milrinone is prohibited. Digitalis is allowed if the patient has been on a stable dose for at least 2 weeks prior to entry into the study.

### **5.3 Dietary restrictions and smoking**

Patients will be domiciled in a hospital setting during the treatment period, and therefore will not be allowed to drink alcohol or smoke during this time.

### **5.4 General restrictions**

Patients will have limited mobility due to the PA catheter during the treatment period.

## **6 Treatment**

### **6.1 Study treatment**

Details on the storage and management of study medication, randomization and instructions for prescribing and taking study treatment are outlined in Section 3 of the Site Operations Manual.

#### **6.1.1 Investigational treatment**

The investigational treatment, CLR325 **Corporate Confidential Information** will be prepared by Novartis and supplied to an unblinded pharmacist at the site as open label bulk medication. The unblinded pharmacist will prepare the appropriate dose depending on the cohort (detailed instructions will be provided in the pharmacy manual). Normal saline will be used as a placebo (will be arranged by sites locally).

Study drugs must be received at the study site by a designated person, handled and stored safely and properly, and kept in a secure location to which only the Investigator and designated staff have access.

Upon receipt, the study drugs should be stored according to the instructions specified on the drug labels. Storage conditions must be adequately monitored and appropriate temperature logs maintained as source data. Appropriate documentation of the subject specific dispensing process must be maintained.

Medication labels will be in the local language, will comply with the legal requirements of each country, and will include storage conditions for the drug but no information about the patient

### **6.2 Treatment arms**

Patients will be assigned to one of the following 2 treatment arms in fixed randomization ratio (CLR325:Placebo):

- Single dose of CLR 325 (i.v.)
- Single dose of Placebo (i.v.)

### **6.3 Permitted dose adjustments and interruptions of study treatment**

Should there be any technical problems with the infusion line (i.e. infiltration, infusion pump malfunction) the infusion must be restarted within 30 minutes or the patient will be considered discontinued from treatment and the infusion shall not be restarted.

Dosage may be discontinued if required to address any safety concerns and should not be restarted. Dose adjustments of study treatment will not be permitted.

### **6.4 Treatment assignment**

Randomization numbers will be assigned in ascending, sequential order to eligible subjects (see Site Operation Manual for details). The randomization number becomes the definitive subject number as soon as a subject receives the first dose of the respective study treatment.

The investigator will enter the randomization number in the eCRF system. The randomization numbers will be generated using the following procedure to ensure that treatment assignment is unbiased and concealed from subjects and investigator staff. A randomization list will be produced by or under the responsibility of Novartis Drug Supply Management using a validated system that automates the random assignment of treatment arms to randomization numbers in the specified ratio. The randomization scheme for subjects will be reviewed and approved by a member of the Novartis IIS Randomization Group.

## **6.5 Treatment blinding**

The sponsor will be unblinded to treatment during this study. Patients, investigator staff, and persons performing the assessments will remain blind to the identity of the treatment from the time of randomization until database lock, using the following methods:

1. Randomization data are kept strictly confidential until the time of unblinding, and will not be accessible by patients, site staff, and study investigators with the exception of the unblinded site pharmacy staff.
2. The identity of the treatments will be concealed by the use of study drugs that are all identical in packaging, labeling, and schedule of administration.

See the Site Operation Manual for further details on blinding.

Unblinding will only occur in the case of subject emergencies ([Section 6.6](#)) and at the time of the interim analysis (see [Section 3.5](#)) and at the conclusion of the study. An assessment will be done by the appropriate site personnel and the sponsor for any subject whose treatment code has been broken inadvertently or for any non-emergency reason to assess whether or not study drug should be discontinued.

